4.2 COVID-19 Surveillance

Surveillance for COVID-19 symptoms will be conducted throughout the study. If a participant experiences any of the symptoms listed below, he or she is instructed to contact the study site immediately and participate in an in-person or telehealth visit as soon as possible, optimally within 3 days of symptom onset (and at the latest 4 days after symptom resolution). To confirm the diagnosis, SARS-CoV-2 test (PCR/ or rapid antigen test) should be performed as soon as possible. Participants who test positive for COVID-19 will be discontinued from further vaccination. During the 7 days following each vaccination, potential COVID-19 symptoms that overlap with solicited systemic events (i.e., fever, chills, new or increased muscle pain, diarrhea, vomiting) should not trigger a potential COVID-19 illness visit unless, in the investigator's opinion, the clinical picture is more indicative of a possible COVID-19 illness than vaccine reactogenicity.

Participants will be provided diary cards to record any symptoms.

In Phase 1b, nasopharyngeal swabs samples for SARS-CoV-2 testing will be collected in duplicate with one sample to be used for the PCR/ or rapid antigen test and the second sample stored (frozen) for possible sequencing of viral RNA if SARS-CoV-2 virus is detected.

Clinical Criteria for COVID-19 (CDC - COVID-19 Interim Case Definition, Aug. 5, 2020): In the absence of a more likely diagnosis, at least two of the following symptoms:

- fever (measured or subjective)
- chills
- rigors
- myalgia
- headache
- sore throat
- nausea or vomiting
- diarrhea
- fatigue
- congestion or runny nose

OR

Any one of the following symptoms:

- cough
- shortness of breath
- difficulty breathing
- new olfactory disorder
- new taste disorder

OR

Severe respiratory illness with at least one of the following:

- Clinical or radiographic evidence of pneumonia
- Acute respiratory distress syndrome (ARDS)

4.3 Potential COVID-19 Illness Visit (Optimally Within 3 Days After Onset):

An unscheduled potential COVID-19 illness visit and unscheduled potential COVID-19 convalescent visit are required at any time during the study that COVID-19 is suspected.

This visit may be conducted as an in-person or telehealth visit; a telehealth visit involves the sharing of healthcare information and services via telecommunication technologies (eg, audio, video, video-conferencing) remotely, thus allowing the participant and investigator to communicate on aspects of clinical care.

As a participant's COVID-19 illness may evolve over time, several contacts may be required to obtain the following information:

- Record any AEs,
- Record any concomitant medications received by the participant
- If the visit is conducted in person, obtain a nasopharyngeal swab for COVID-19 testing (collected by site staff. For Phase 1b only, collect swabs in duplicate with one swab being stored frozen for possible viral RNA sequencing).
- The participant should be encouraged to seek care or COVID-19 testing, if appropriate, from his or her usual provider.
- Collect COVID-19-related standard-of-care clinical and laboratory information.
- Schedule an appointment for the participant to return for the potential COVID-19 convalescent visit once recovered.

4.4 Early DSMB Study Review and Continuation Criteria

Safety criteria for study continuation

Early DSMB reviews of post-vaccination safety data and stopping rules will be implemented for safety and protection of study participants (see [Section 5.2, Protection of Participants](#), below).

In Phase 1a, the second vaccination will proceed only after the DSMB has confirmed that the vaccine safety and tolerability is acceptable and that stopping rules were not met through 7 days after the first dose.

In Phase 1b, DSMB will review blinded Day 7 safety data after the first 10 participants in each group. Only after the DSMB confirms that safety is acceptable and that stopping rules were not met will the enrollment in the respective study groups continue to its completion.

For details on timing of DSMB reviews, please see [Figure 1](#) above.

Stopping rules

Study vaccinations will stop if 2 or more participants receiving VBI-2902a or VBI-2905a meet the stopping rules criteria (defined in [Section 10.7](#)) unless the DSMB and study sponsor and site investigators review the safety data, and in consultation with the appropriate regulatory authorities, determine that the safety of study participants is not affected and that study vaccination may continue.

Immunogenicity criteria for study continuation

Neutralizing antibody (nAb) titers, determined by pseudovirus microneutralization assay and plaque- reduction neutralization test (PRNT) on serum collected at Day 28 (4 weeks after the first vaccination) and Day 56 (4 weeks after the second vaccination) will be used as the primary determinant for immunogenicity. Additional immunological endpoints, described below, will also be considered as secondary endpoints.

Geometric mean titers (GMT) of nAb and binding antibodies to the spike protein and its receptor binding domain (RBD) in one-dose and two-dose groups in Phase 1a at Days 1, 7, 28, 35 and 56 will be compared against a panel of COVID-19 convalescent sera as well as a WHO International Standard of high titer pooled COVID-19 convalescent sera. Day 28 antibodies to RBD and T-cell endpoints will be considered if Day 56 nAb results do not allow a clear determination of equivalence or superiority. If responses are inferior to that of the panel of convalescent serum in Phase 1a and Phase 1b, neither VBI-2902a nor VBI-2905a will undergo further testing at the proposed dose levels and dose regimens. In Phase 1b, the percentage of subjects with a 4-fold or greater increase in nAb titers will be determined, as this represents a meaningful boosting of immunity.

The group sizes will allow determination of at least two-fold differences in nAb titers at a power of 80% with an alpha error of 0.05. Safety and tolerability will be evaluated in the total of ~67 participants who will receive at least one dose of VBI-2902a or VBI-2905a and in ~47 participants who will receive placebo. If no safety signals are detected and immunogenicity is demonstrated, further clinical development will be considered. Further clinical development may not be considered if optimal nAb titers are not equivalent to or superior to that of the panel of COVID- 19 convalescent serum. The safety, tolerability and percentage of subjects with 4-fold or greater increases in nAb titers at Days 28 and 56 will be used to determine whether further clinical development of a one-dose vaccination regimen is justified.

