	
Stopping rules - study vaccinations will stop if 2 or more participants receiving VBI-2902a or VBI-2905a meet stopping rules criteria unless the DSMB and study sponsor and site investigators review the safety data, and in consultation with BRDD, determine that safety of study participants is not affected and that study vaccination may continue.
 
Immunogenicity criteria for study continuation
 
Neutralizing antibody (nAb) titers, determined by pseudovirus microneutralization assay and plaque-reduction neutralization test (PRNT) on serum collected at Day 28 (4 weeks after the first vaccination) and Day 56 (4 weeks after the second vaccination) will be used as the primary determinant for immunogenicity, and will determine whether the study will proceed to Phase 1b. Additional immunological endpoints, described below, will also be considered as secondary endpoints.
 
Geometric mean nAb titers and binding antibodies to spike protein and its receptor binding domain (RBD) in one-dose and two-dose groups in Phase 1a at Days 1, 7, 28, 35 and 56 will be compared against a panel of COVID-19 convalescent sera as well as a WHO International Standard of high titer pooled COVID-19 convalescent sera. A non-inferior GMT nAb titer against the GMT of the panel of COVID-19 convalescent sera (tested against the original Wuhan strain PNA for phase 1a participants and against the B.1.351 variant PNA in phase 1b) in subjects receiving 2 doses of VBI-2902a will justify proceeding to Phase 1b; comparison of the nAb GMT against the WHO reference standard will be used to aid benchmarking against other COVID-19 vaccine candidates. Day 28 antibodies to RBD and T-cell endpoints will be considered if Day 56 nAb results do not allow a clear determination of equivalence or superiority to the convalescent sera neutralizing antibody GMTs. If responses are inferior to that of the panel of convalescent serum, neither VBI-2902a nor VBI-2905a will undergo further testing at the proposed dose levels and dose regimens. In Phase 1b the percentage with a 4- fold or greater increase in nAb titers following vaccination will be determined, as this represents a meaningful boosting of immunity.
 
The group sizes will allow determination of at least two-fold differences in nAb titers at a power of 80% with an alpha error of 0.05. Safety and tolerability will be evaluated in the total of ~67 participants who will receive at least one dose of VBI2902a or VBI- 2905a and in ~47 participants who will receive placebo. If no safety signals are detected and immunogenicity is demonstrated, further clinical development will be considered.
 
Further clinical development may not be considered if nAb titers are not equivalent to or superior to that of the panel of COVID-19 convalescent serum. The safety, tolerability and percentage of subjects with 4-fold or greater increases in neutralizing antibody titers at Days 28 and 56 will be used to determine whether further clinical development of a one-dose vaccination regimen is justified.

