4.6 Subject Selection and Sample Size

A total of approximately 60 participants will be enrolled in Phase 1a and approximately 54 participants in Phase 1b. Participants in Phase 1a will be randomized at 2:1 to VBI-2902a or placebo. Participants in Phase 1b will be randomized at 1:1 to receive one dose of VBI-2905a or placebo.

The Phase 1a and Phase 1b parts of the study are being conducted at clinical sites in Canada. For the Phase 1b part of the study, the sites will only enroll participants who have previously received mRNA COVID-19 vaccines.

With ~10% drop-out rate it is estimated that at least 56 participants will complete Phase 1a and 48 participants will complete Phase 1b. The sample size per active group will allow for the detection of at least a two-fold difference in nAb titers with 80% power and an alpha error of 0.05.

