4.8 Treatment Allocation

Phase 1a

In Phase 1a, VBI-2902a at a dose of 5 µg will be administered to participants 18-54 years of age. An Independent Data Safety Monitoring Board (DSMB) will perform an early review of blinded post-vaccination safety data at Day 7 after the first vaccination (reactogenicity, AEs and safety labs). The second vaccination will be given only if the DSMB confirms that early safety is acceptable and that stopping rules were not met.

The DSMB will further review blinded post-vaccination safety through Day 35, 7 days after the second vaccination and through Day 56, 28 days after the second vaccination. Enrollment in Phase 1b will commence once the DSMB confirms that safety data through Day 56 is acceptable and that stopping rules were not met.

The Study Steering Committee (SSC), comprised of representatives from the study sponsor (not involved in study operations) and external vaccine experts, will review unblinded immunogenicity data inclusive of Day 35, i.e., 35 days after the first (7 days after the second) vaccination, as well as Day 56, i.e., 56 days after the first (28 days after the second) vaccination from Phase 1a. Based on the pre-specified criteria for primary and secondary safety and immunogenicity endpoints, the Phase 1b dose and regimen of VBI-2905a may be modified.

Phase 1b

Phase 1b will evaluate the safety, tolerability and immunogenicity of a one-dose regimen of VBI-2905a at a dose level of 5 µg of S protein in healthy adults aged 18-54 years. DSMB will review blinded Day 7 safety data after the first 10 participants in each group have received their dose. Only after the DSMB

confirms that safety is acceptable and that stopping rules were not met will the enrollment in the respective study groups continue to its completion.

The SSC will review unblinded immunogenicity data 7 days and 28 days after the first vaccination,. Study participants will continue with study visits as planned up to 12 months of follow up after the first dose of study vaccine.

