4.13 Immunogenicity Assessments

Immunogenicity will be assessed by measuring serum nAb titers against wild-type SARS- CoV-2 virus (PRNT) and/or spike protein-expressing pseudovirus (microneutralization), serum binding antibody titers against spike protein and the spike protein receptor-binding domain (RBD) and peripheral blood mononuclear cell (PBMC) T cell responses against spike protein. Testing will include assessment of responses against spike protein of the original SARS-CoV-2 isolate as well as spike protein of variant Beta (B.1.315) and other variants. In Phase 1a, time points for evaluation will be at Study Days 1, 7, 28,

35, 56, 112, 224 and 336. In Phase 1b, time points for evaluation will be at Study Days 1, 7, 14, 28, 56, 84, 168 and 336. Neutralizing antibody and binding antibody results will be presented as the geometric mean titer (GMT) and the geometric mean fold increase in titer post-vaccination over baseline. T cell responses will be presented as the geometric mean number of IFN- γ ELISPOT-positive cells per 10^6 PBMCs.

A non-inferior GMT nAb titer against the GMT of the panel of COVID-19 convalescent sera (tested against the original Wuhan strain PNA for Phase 1a participants and against the B.1.351 beta variant PNA in Phase 1b) in subjects receiving 2 doses of VBI-2902a will justify proceeding with further clinical development; comparison of the nAb GMT against the WHO reference standard will be used to aid benchmarking against other COVID-19 vaccine candidates.

Similarly, the immunogenicity of VBI-2905a booster in previously vaccinated will be assessed in G4 participants by comparing it to G5 participants. A four-fold increase in the post-boost neutralizing antibody titer in the beta variant PNA will be considered as a confirmatory benchmark to advance clinical development of the 2905a vaccine candidate. If the results are not confirmatory, then the analysis of the RBD ELISA and IgG and T cell data will be undertaken by the SSC to make a decision to further the development of 2905a.

Immunogenicity results will be presented descriptively as point estimates and 95% confidence intervals (CIs), which will be tabulated by study group. Exploratory immunogenicity endpoints may include GMTs against variants of concern, as well as additional markers for T cell responses by ELISPOT and serum binding IgG subclasses as a marker of Th1 (IgG1 and IgG3) and Th2 (IgG4) dominated responses.

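### The immunogenicity go/no-go rule differs between the synopsis and Sections 4.4, 4.8 and 4.13, and its Phase 1b limb cannot separate VBI-2905a from prior mRNA vaccination

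*Protocol*

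**What the plan says.** The protocol states the immunogenicity criteria for continuing in four places, and they do not agree.

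- **Section 4.4** carries a binding stop, which ends testing of both candidates at the planned doses and regimens and begins: "If responses are inferior to that of the panel of convalescent serum in Phase 1a and Phase 1b, neither VBI-2902a nor VBI-2905a will undergo". The next paragraph adds a discretionary criterion with no phase condition: "Further clinical development may not be considered if optimal nAb titers are not equivalent to or superior to that of the panel".
- **Synopsis, Study Continuation Criteria**, gives the stop without a phase: "If responses are inferior to that of the panel of convalescent serum, neither VBI-2902a nor VBI-2905a will undergo further testing". It also says that the Day 28 and Day 56 titers "will determine whether the study will proceed to Phase 1b". Section 4.4 omits that entry condition.
- **Section 4.8** rests entry on safety: "Enrollment in Phase 1b will commence once the DSMB confirms that safety data through Day 56 is acceptable". The steering committee also sees Day 35 and Day 56 immunogenicity data, but the stated consequence is a possible change to the Phase 1b dose and regimen.
- **Section 4.13** makes non-inferiority to the panel the positive criterion, with the Wuhan assay for Phase 1a and the Beta assay for Phase 1b, but attaches both to one group: "against the B.1.351 beta variant PNA in Phase 1b) in subjects receiving 2 doses of VBI-2902a will justify proceeding with further clinical development". It then says that "the immunogenicity of VBI-2905a booster in previously vaccinated will be assessed in G4 participants by comparing it to G5 participants", and names a four-fold rise in the Beta assay as the confirmatory benchmark, with steering committee review of other data if that is not met.

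Section 4.6 says of Phase 1b that "the sites will only enroll participants who have previously received mRNA COVID-19 vaccines". Section 5.1 requires two doses, at least four 28-day months before enrollment.

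**The concern.** A comparison with convalescent sera is a single-group benchmark. In naive participants, such as G2, the post-vaccination titer can be credited to the study vaccine. In Phase 1b it cannot. A G4 titer is the sum of mRNA priming and whatever VBI-2905a adds, and G5 carries the same priming with no study antigen. If VBI-2905a added nothing, G4 and G5 would have the same chance of passing or failing against the panel.

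Section 4.4 joins that confounded comparison to the interpretable one. Taken literally, the binding stop needs inferiority in both phases. VBI-2902a could then be inferior in naive adults, and the stop would not be triggered because mRNA-primed people given a different product were not inferior. Under the synopsis the same data would stop the programme, or Phase 1b would not have opened.

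With conflicting triggers and no definition of inferior, the development decision can be argued either way once titers are unblinded.

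**Working it through.** **The plan's own figure.** The only statistical figure attached to these criteria is detection of a two-fold difference with 80% power at alpha 0.05. No SD is given, so it cannot be reproduced directly. Solving for the largest log10 SD that supports it, two-sided with two equal groups, SD = log10(2) / [√(2/n) × (1.960 + 0.842)]:

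- n = 20: 0.301 / (0.3162 × 2.802) = 0.34; n = 18 completers: 0.32
- n = 27: 0.301 / (0.2722 × 2.802) = 0.395; n = 24 completers: 0.37

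This concerns two equal groups. It says nothing about a comparison with a panel of unstated size, and the stop rule itself carries no number.

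**Operating characteristics of the stop.**

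*From the documents:* about 10% dropout leaves 20 × 0.9 = 18 in G2; 48 Phase 1b completers leave 48 / 2 = 24 in G4.

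*Assumed, because no document states them:* log10 SD 0.3 to 0.5; a panel of m = 20 to 40 sera; a true Phase 1a ratio to the panel of 0.5 (the two-fold difference the plan names); inferior taken to mean that the upper 95% limit of the GMT ratio is below 1; phases independent given the panel.

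For true ratio r and group size n:

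- se = SD × √(1/n + 1/m)
- P(inferior) = Φ(−log10(r)/se − 1.96)
- two-phase rule: P(stop) = P(inferior in 1a) × P(inferior in 1b)

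Worked case, SD 0.4, m = 20:

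- Phase 1a: se = 0.4 × √(1/18 + 1/20) = 0.130; Φ(0.301/0.130 − 1.96) = Φ(0.356) = 0.639
- Phase 1b, r = 1: Φ(−1.96) = 0.025; product 0.016
- Phase 1b, r = 0.5: se = 0.4 × √(1/24 + 1/20) = 0.121; Φ(0.526) = 0.700; product 0.448

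| SD | Panel | Phase 1a alone | Both, 1b ratio 0.5 | Both, 0.75 | Both, 1 | Both, 2 |
|---|---|---|---|---|---|---|
| 0.3 | 20 | 0.870 | 0.794 | 0.243 | 0.022 | <0.001 |
| 0.3 | 40 | 0.942 | 0.917 | 0.343 | 0.024 | <0.001 |
| 0.4 | 20 | 0.639 | 0.448 | 0.113 | 0.016 | <0.001 |
| 0.4 | 40 | 0.755 | 0.627 | 0.171 | 0.019 | <0.001 |
| 0.5 | 20 | 0.457 | 0.234 | 0.059 | 0.011 | <0.001 |
| 0.5 | 40 | 0.564 | 0.364 | 0.091 | 0.014 | <0.001 |

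**Sensitivity to the missing definition.** If inferior instead means that non-inferiority was not shown at an assumed margin of 0.67, then P = 1 − Φ([log10(r) − log10(0.67)]/se − 1.96). Over the same SDs and panel sizes the two-phase rule fires with probability 0.39–0.79 at a Phase 1b ratio of 1, and at most 0.12 at 2. At a ratio of 1, moving between two ordinary definitions takes the rule from about 1–2% to 39–79%.

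**Does the SAP settle it?** No. Section 6.4.1 still describes 5 and 10 µg groups compared with pooled convalescent serum. Section 6.4.2 specifies pairwise comparisons between treatment groups and no panel comparison. Neither gives a margin.

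**The case against.** A reader might infer that the stop is close to inoperative and that placebo recipients would meet the benchmark. The documents do not support that. The Phase 1b benchmark is in the Beta assay, at least four months after priming, and Section 2.1 says protection against variants can be weaker than against the Wuhan strain, so a primed titer below the panel is plausible. Take SD 0.4, a panel of 30, 27 per arm, a 1.5-fold margin and one-sided 2.5%, all assumed except the arm size. Then se = 0.4 × √(1/27 + 1/30) = 0.106, and the chance that G5 is declared non-inferior, Φ([log10(1.5) + log10(k)]/se − 1.96), is 38% at k = 1, 91% at 1.5 and 99% at 2 times the panel. It is only 7% at 0.75 and 0.1% at 0.5. That calculation also models placebo passing, which is a different event from vaccine responses being inferior.

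The wording of Section 4.4 can also be read distributively, each phase against its own benchmark. Even as a conjunction, it says when both candidates stop, not that one failing alone must continue. Other criteria limit the consequence: the synopsis entry condition, the discretionary criterion in Section 4.4, and in Section 4.13 the G4-versus-G5 comparison and four-fold benchmark. Primary endpoints are safety, and Section 10.3 calls immunogenicity results exploratory.

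Most of this stands, and it limits the severity. It does not remove the point. The distributive reading leaves the Phase 1b limb confounded and the two candidates tied together. The other criteria are discretionary or conflict with one another, and Section 4.13 does not amend Section 4.4. Exploratory or not, the protocol uses these titers to decide development.

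**Conclusion.** The concern holds as an inconsistency in a stated decision rule, with one limb that cannot be interpreted. Three things follow from the text alone: the binding stop has two different triggers; entry to Phase 1b rests on titers in one place and on the safety review in another; and the Phase 1b panel criterion names a group that Phase 1b does not contain. That a G4-versus-panel result cannot be credited to VBI-2905a follows from the eligibility criteria.

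The size is conditional. With Phase 1a titers at half the panel, the literal two-phase rule fires about 1–2% of the time if the Phase 1b ratio is 1 and 23–92% if it is 0.5, against 46–94% for a rule on Phase 1a alone. These ranges rest on an assumed SD, panel size, ratios and definition of inferior. Independence is approximate, because both phases may share a panel source. The deciding quantity, the primed Beta titer relative to the panel, is not in the documents, so no claim that the stop would never fire can be made.

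Severity: should-fix. No randomised comparison, primary endpoint or safety stopping rule is affected.

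**What to change.** Reconcile the synopsis and Sections 4.4, 4.8 and 4.13 into one rule, stated separately for each candidate, and replace the clause that ties VBI-2902a and VBI-2905a together. Deleting only the reference to Phase 1b in Section 4.4 would not do: it would bar VBI-2905a on a VBI-2902a result.

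- **VBI-2902a:** decide on G2 at Day 56 against the panel in the Wuhan pseudovirus assay. Define inferior by a stated margin and confidence level, and describe the panel (number and source of sera).
- **VBI-2905a:** decide on the randomised G4-versus-G5 comparison in the Beta pseudovirus assay, together with the four-fold benchmark already in Section 4.13. State the time point, and whether four-fold refers to the geometric mean rise or to the proportion of participants reaching it, since Section 4.4 speaks of the latter.
- **Panel in Phase 1b:** keep as descriptive context only, and remove the reference to two-dose VBI-2902a recipients from the Phase 1b criterion.
- **Entry to Phase 1b:** state in one place whether it depends on Phase 1a titers, the safety review, or both.
- **SAP:** bring Section 6.4.1 into line and add the G2-versus-panel comparison. Section 6.4.2 already plans the pairwise group comparisons.

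The cost is wording. No new data are needed, since G5 is already randomised at 27. The rule becomes stricter for VBI-2902a.
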